3.4.1 BASELINE ASSESSMENTS

Prior to commencing the ketogenic diet, participants will be required to attend for initial baseline assessments, to include venepuncture and brain imaging. It is likely that this will take place over two separate days, with the venepuncture and brain imaging occurring on the second attendance. The research team will try to minimise the number of journeys for patients and reimburse any travel costs. It will be important for the baseline assessments to all be within a few days of each other to allow initiation of the diet as soon as possible after venepuncture, brain imaging, and receiving advice on initiating the diet.

Participants will be seen by a psychiatrist at the clinical research facility (CRF) in Edinburgh, for an appointment lasting around 2 hours. They will gain written consent if the patient wishes to continue and after any questions or concerns have been addressed (around 10 minutes). They will then collect basic demographics to include age, sex, highest educational qualification, and total household income (around 10 minutes).

They will then administer the following questionnaires (around 1 hour):

- MINI Neuropsychiatric interview (modules A-D and L) a structured diagnostic interview based on DSM-4 criteria to confirm BD diagnosis and current mood episodes
- Affective Lability Scale (ALS-18) a self-reported measure of mood instability
- Beck Depression Inventory (BDI) a self-reported measure of depressive symptoms
- Young Mania Rating Scale (YMRS) a self-reported measure of hypomanic/manic symptoms
- EQ5D-5L health economics Quality of Life instrument

- Work Productivity and Activity Impairment Questionnaire (WPAI) health economics questionnaire
- Within Trial Resource Use Questionnaire health economics questionnaire

After completing the questionnaires, participants will have their height, weight and blood pressure measured (around 10 minutes). This means they will have been at rest for around an hour when their blood pressure if checked. They will be provided with instruction on the use of a wrist-worn actigraph to record sleep and activity, which will be worn throughout the 10-week study period (around 10 minutes). They will be provided with education on the use of a glucose and ketone measuring device, to allow participants to measure both parameters every day during the 10-week study period (around 10 minutes). This will allow us to monitor adherence to the diet and explore any correlation of these markers with regular mood assessments. We will ensure the participant is comfortable with using both devices, including how to dispose of used lancets into sharps boxes, which will be provided to them, and how and where to record the results, which will be in an app on their phone (around 10 minutes).

Participants will also be familiarised with the ilumivu app to allow them to record their mental state via ecological momentary assessments (a simple scoring system which should take about 5 - 10 minutes to complete). This will entail using a simple visual analogue scale from 1-100 to record their mood, energy, speed of thought, impulsivity, and anxiety on a daily basis, which will take 5-10 minutes. Participants will be taught to set a daily alarm in the app to remind them to do this. Participants may be asked to download both phone apps prior to attending their first face-to-face appointment if they are able.

If it is not possible to use the ketomojo or ilumivu apps, the study team will instead establish a texting or telephone call system. If this is the case, participants will be texted or called each day to ask them to provide their ketone and glucose readings, and elements of their mental state on a scale of 1-100. Even if the apps are used as the method for collecting this data, the team may still use texting as a way to remind participants to fill in these parameters on the apps if they are forgetting to do this. Participants will be informed of the correct process at their baseline appointment.

The participant will see a dietitian who will provide detailed information about establishing and maintaining the KD. Participants will receive education around how to do this, based on resources from the KD service already in place in Edinburgh.

Participants will also have venous blood samples taken to be sent for biochemistry and metabolomics, following the specific procedures required by each department. This will either be undertaken by a psychiatrist on the research team, or by staff at the clinical research facility, who will support the research team. Venous blood samples will likely be taken at a second visit (around 10 minutes), when participants attend for brain imaging (see below). They will need to fast prior to these.

Metabolomic blood samples will be taken and processed at the CRF and frozen at -80. Plasma and cell samples will then be sent to another CRF lab for extractions (see separate protocols). The extracts will then be sent to University of Edinburgh metabolomics department for analysis (see study protocol). Serum samples will also be kept in case we need these in future for more advanced metabolomic analysis. All of these samples will be labelled with participant ID number only, and the University of Edinburgh lab will not have access to any personal identifiable information.

Biochemistry blood samples will be sent to the Royal Infirmary of Edinburgh laboratory for U&Es, LFTS, lipid profile, HbA1c, CRP, beta-hydroxybutyrate, insulin and fasting glucose. The fasting glucose and insulin will be used to calculate HOMA-IR, a measure of insulin resistance. The samples will be processed by the local laboratory who will assign the study a number. They will be processed using the participants CHI number and will be available to view in their medical records, which participants will be informed of. Results will be reviewed and signed off by a member of the research team within 48 hours.

Participants may find the blood tests uncomfortable and/or distressing in the event of a needle phobia, and may experience minor bruising. It will be explained prior to taking blood what patients can expect. A chaperone will be offered if the patient would find this reassuring, provided by the Clinical Research Facility (CRF). The researcher will be an experienced phlebotomist and apply pressure to avoid bruising.

The participant will also attend the Royal Infirmary of Edinburgh for an MR spectroscopy (a type of brain scan) (around 1 hour). This is non-invasive and will not require injection of any substances. This will allow us to measure metabolic markers in the brain and compare these before and after the intervention. Please see imaging data analysis section for more information. All standard imaging service procedures will be followed.

Participants may find MRI brain scans anxiety provoking and may experience claustrophobia during the scans. The research team will ensure that the procedure is explained to participants, so they know what to expect. The research co-ordinator will attend this appointment with participants if necessary and appropriate. If any incidental findings occur, the participants GP will be informed.

Participants will be fully informed about what all the above assessments and interventions entail in both the PIS, and through discussions with the research team. The research team will spend time ensuring participants fully understand all aspects of the study, and how to use all the devices before they are expected to use them themselves. They will also be contactable by participants throughout the study.

3.4.2 FOLLOW UP ASSESSMENTS

Participants will attend for repeat venepuncture and brain imaging in week 6, 7, or 8 of the 8-week intervention period. They will need to be fasted prior to this and will follow the same process as the baseline venepuncture and brain imaging. A psychiatrist will then repeat the baseline questionnaires and physical parameters as detailed above. The dietitian will clarify with them if they plan to continue the KD. If they do plan to continue the dietitian will provide further advice about how to do this. The dietitian will also be available for a further 4 weeks following the end of the 10-week study period, to provide ongoing advice and support if participants plan to continue the KD. We will aim for all follow up assessments to take place during one appointment.

Participants will be asked to monitor glucose and ketone measurements every day, wear their actigraph device, and record mood daily for the full 10-week study period. This will apply if they decide to stop the diet after 8 weeks or if they have decided to continue the diet. This will allow us to see if there are any changes in these parameters related to stopping the diet.

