3.3 KETOGENIC DIET INTERVENTION

All study participants will receive a low-carbohydrate, high-fat ketogenic diet intervention for an 8-week period, the first 2 weeks of which will be an adaptation period. The 8 weeks will then be followed by a 2-week cessation period. They will continue usual medical treatment from their regular care teams, including mental health services.

Based on the successful experience of the study dietitians in administering the KD to adults with epilepsy, we will identify a KD formulation associated with good levels of adherence. We will work closely with Patient and Public Involvement (PPI) representatives from Bipolar Scotland to develop and refine materials to support patients in adopting this diet.

Participants will have an initial meeting with a dietitian, lasting up to 2 hours, to discuss the details of the diet, food preferences, monitoring, and potential risks. They will request that participants complete a food diary to bring to their first appointment, to help plan what meals may be most appropriate for them to try on a KD. This will involve recording everything they eat and drink for 3 days prior to attending. International guidelines for the management of adults treated with ketogenic diet therapies (Mackenzie 2021) suggests that 'preparation and training must be individualised to provide the greatest likelihood of success', and we will endeavour to make this is a key part of our dietary initiation.

The diet will be gradually introduced over a 2-week period. Support will be via dietary supervision over the first few days to check adherence to prescribed diets, problem solve and identify any adverse effects, which will mainly occur over the phone or via email. Dietitians will provide guidance and practical support around establishing and characterising the diet, using recipe cards and planning, dietary booklets and providing advice on common problems. We will have support from a Professor of Behavioural Science to develop our approach to behavioural aspects of the intervention including barrier identification, problem solving, habit formation, social support, reducing negative emotions, and restructuring the environment.

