4 STUDY POPULATION

4.1 NUMBER OF PARTICIPANTS

This study will aim to recruit 25 patients meeting the study criteria and consenting to take part.

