10 STATISTICS AND DATA ANALYSIS

10.1 SAMPLE SIZE CALCULATION

No formal sample size was calculated as this is a small feasibility study. We are not planning to draw firm conclusions about the efficacy of the diet.

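### Questionnaires, weight and blood pressure are not planned under matched conditions before and after the diet: fasting state and order relative to the MRI differ

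*Protocol*

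**What the plan says.** **Baseline (Protocol 3.4.1).** On the split of visits: "It is likely that this will take place over two separate days, with the venepuncture and brain imaging occurring on the second attendance". The psychiatrist's appointment covers consent, demographics and the questionnaires (MINI, ALS-18, BDI, YMRS, EQ5D-5L, WPAI, resource use). Physical measures come next: "After completing the questionnaires, participants will have their height, weight and blood pressure measured". The section notes that this gives about an hour of rest before blood pressure. Fasting is required only for the blood samples, which are likely to be taken at the second visit together with imaging. Nothing is said about eating before the psychiatrist's visit.

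**Follow-up (Protocol 3.4.2).** Participants return in week 6, 7 or 8, fasted, for venepuncture and imaging, using the baseline process for those two procedures. Then: "A psychiatrist will then repeat the baseline questionnaires and physical parameters as detailed above". On timing: "We will aim for all follow up assessments to take place during one appointment".

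**The scan.** Section 3.4.1 allows about an hour for it and warns: "Participants may find MRI brain scans anxiety provoking and may experience claustrophobia during the scans".

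**Design and use.** Section 3.3: "All study participants will receive a low-carbohydrate, high-fat ketogenic diet intervention for an 8-week period". Section 2.3 lists among the primary objectives a before-after look for early indications of efficacy on mood instability, quality of life and function, and a description of the spread of outcome values for the future trial. Section 10 limits this: the analysis of change is descriptive and no firm efficacy conclusion is intended.

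**The concern.** A before-after difference in a single arm is interpretable only as far as the two measurements are taken in the same way. Section 3.4.2 protects this for blood and imaging by repeating the baseline process. It gives no equivalent protection for fasting state or order when it comes to the questionnaires and physical measures. Read as planned, those measures move from a visit with no fasting instruction and no scan to a point after a fasted blood draw and an MRI.

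No control group goes through the same change of conditions, so nothing cancels its effect. Descriptive analysis does not remove a systematic shift, and more participants would not either.

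Two uses are exposed. One is the before-after description of mood, quality of life and function. The other is the pilot's role in handing visit procedures and outcome spreads to a future trial. Weight matters as well, although it is not a listed outcome in sections 2.5 and 2.6. It is collected before and after (section 8), weight loss is a named side effect (section 3.3), and reporting adverse effects is a primary objective.

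**Working it through.** The protocol states no effect size, SD, alpha or power (section 10.1: "No formal sample size was calculated as this is a small feasibility study"), so there is no planned figure to reproduce. The main check is a comparison of the two visits.

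| Condition | Baseline (3.4.1) | Follow-up (3.4.2) |
|---|---|---|
| Attendances | likely two days | one appointment, as an aim |
| Fasting before questionnaires, weight and BP | no instruction | participants arrive fasted for blood and MRI |
| Order relative to blood and MRI | earlier, likely on another day | afterwards |
| Rest before BP | about an hour, during the questionnaires | about an hour if the baseline sequence is kept |

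Three of the four rows differ as planned. The fourth is matched if the reference back to the baseline procedure is followed.

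**What an unremoved shift would do (illustration; the shifts are assumptions).** The planned n is 25 (section 4.1); n = 20 is an assumed attrition case. Let d be the shift due to conditions alone, in SDs of the change score, with no diet effect.

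- Half-width of the 95% interval for a mean change, in SDs of the change: t(0.975, n−1)/√n. For n = 25 this is 2.064/5 = 0.413. For n = 20 it is 2.093/4.472 = 0.468.
- Probability that the interval excludes zero: P(|T| > t(0.975, n−1)), with T noncentral t on n−1 degrees of freedom and noncentrality d√n.

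| Assumed d | n = 25 | n = 20 |
|---|---|---|
| 0 | 0.05 | 0.05 |
| 0.1 | 0.077 | 0.071 |
| 0.2 | 0.161 | 0.136 |
| 0.4 | 0.484 | 0.397 |

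For any fixed d above zero the probability is higher at 25 than at 20: a larger sample makes the artefact easier to detect but does not remove it. The protocol plans no such interval or test. The table shows only how a reader's own interval would behave.

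**Weight (both inputs are assumptions).** Suppose a fasted weight is 0.5 to 1.5 kg below a non-fasted one and the true loss on the diet is 3 to 6 kg. The spurious part, relative to the true loss, runs from 0.5/6 = 8% to 1.5/3 = 50%. The upper end pairs the largest shift with the smallest loss. The two other corners are 0.5/3 = 17% and 1.5/6 = 25%.

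**The case against.** The case against a stronger claim is substantial, and most of it stands.

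- A reader might infer that every baseline value is taken fed and every follow-up value fasted and straight after the scan. The documents do not say so. The first visit is silent on eating, the two-day baseline is only likely, and the single follow-up appointment is an aim. The follow-up wording gives sequence, not immediacy, and does not bar a meal or break after the scan.
- Blood pressure is partly protected. If the baseline sequence is repeated, it again follows about an hour of questionnaires at rest.
- A reader might also infer that the protocol will present the difference as a diet effect. Section 10 disclaims firm efficacy conclusions and plans description only, and weight and blood pressure are not listed outcomes. Only the early-efficacy objective in section 2.3, which covers mood, quality of life and function, invites that reading.
- Mood, energy, speed of thought, impulsivity and anxiety are rated daily outside the clinic, unaffected by visit order. This is a real safeguard for mood, though it does not replace the ALS-18, BDI, YMRS, EQ5D-5L or WPAI.
- The flowchart and participant infographic cited in section 3.4 are not at hand and may settle the order.

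What remains is that the protocol text plans different conditions, does not fix them, and does not list fasting state or order among the case report form contents in section 8.2. If practice varies between participants, the difference becomes unrecorded noise in the change scores rather than a uniform shift.

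**Conclusion.** The point holds in a limited form. As planned, the questionnaires, weight and blood pressure are not taken under the same conditions before and after, and the single-arm design cannot separate a resulting shift from the diet. Weight is the clearest case. Blood pressure is a weak case if the hour of rest is kept.

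For mood and quality of life, neither size nor direction can be taken from the documents. It is tempting to say that hunger and scan anxiety would worsen everyone's scores and hide a benefit. The protocol says only that participants may find the scan anxiety provoking, so a common direction is not supported.

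The figures above rest on assumed shifts and show sensitivity, not an estimate of bias. For a 25-person descriptive pilot this does not threaten the feasibility aims. It is an avoidable flaw in the before-after comparison, worth correcting because correction is cheap and the schedule is meant to inform a later trial.

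**What to change.** 1. Take weight and blood pressure at the fasted blood and MRI attendance at both time points, at the same point in the visit. State the rest period before blood pressure and keep it the same. At present the questionnaires supply that rest at baseline, so it must be written in once the measurement moves.
2. Amend the sentence in section 3.4.2 that places the questionnaires after blood and imaging. Follow-up questionnaires should be done either at a separate attendance, as is likely at baseline, or after a meal and rest break once blood and scan are complete. The first option matches baseline more closely but gives up the single appointment. The second removes the fasting difference but leaves the questionnaires after the scan.
3. Leave the fasted state for blood and imaging unchanged. Feeding participants before the scan so as to do the questionnaires first would disturb the matched conditions for spectroscopy, whose lactate and ketone-related measures are the primary imaging outcome (section 3.6).
4. Record fasting state and order relative to the scan on the case report form at both time points, and state any remaining difference as a limitation.

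Cost: about 10 minutes of measurement moved to the second baseline visit, plus the stated rest period, and a slightly longer follow-up day (or one further journey if the separate attendance is chosen). No new procedure is needed.

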3.4.3 DATA COLLECTION

Data from the ilumivu app will be accessible to the research team, and will be reviewed at least weekly for each patient. This is a research app, and the platform does not require any patient identifiable data, using only the participant's study number to enter into their mobile app.

The ilumivu app is produced by a company called ilumivu which is a decade old software company. The app is based on ecological momentary assessments, a method for collecting data from people as they go about their daily lives giving you access to what is really happening in the moment. It allows researchers to create their own surveys and notification schedules that can be standardised for a group. In this research study, participants will be asked to rate their mood, energy, speed of thought, impulsivity, and anxiety on a visual analogue scale from 0-100, on a once daily basis.

It is a cloud-based system which provides software maintenance, data security and backups. The technology logistics are managed by the ilumivu company. The platform does not require any personally identifying information from participants. It automatically generates a unique identifying code that the user enters into their mobile app. The key linking this code to personal identifiable information is stored outside the system by the research team. All data collected from the apps are encrypted before being pushed to the cloud-based storage database. No data are ever stored on the server's file server but always in the database. Access to the database is gated so entry is only permitted to users entering through the approved route (i.e. you can't hack your way into the database by guessing at the URL), and after supplying a verified user ID and password. For clients in Europe, there are servers in the Netherlands. Data are made accessible to the researchers only by directly accessing the secure site with their verified login credentials and downloading the dataset as a CSV file onto a secure server. Individual datasets will never be transmitted by email. An agreement is in place and the invoice for its use has been paid. Data collected via the Ilumivu app will be processed in the USA, outside of GDPR compliant zone, but will not include any personal identifiable data.

Participants will take ketone and glucose readings on their "KetoMojo" device. The device will be synced via Bluetooth to the KetoMojo phone app. This data is then synced to MyMojoHealth a secure, cloud-based, double encrypted, HIPAA-compliant data storage database with servers based in Europe. Practitioners can access and review patient data directly through a MyMojoHealth practitioner account. The ketomojo app will collect personal data, namely first name, second name and email address, and third parties will have access to general usage analytics such as metrics about what parts of the apps are used.

NHS Lothian cannot guarantee the safety of participants information on their own device when accessing the ketomojo and ilumivu apps.

If it is not possible to collect data via the above apps, a texting or telephone call system will be established by the research team to collect this data. Only UoE or NHS phones will be used, and participants numbers will be stored in these using their study ID number only. They will be sent generic messages which will not include personal identifiable information, and they will be reminded not to disclose any such information when sending replies. They will be asked only for data described above, namely ketone and glucose readings and ratings for aspects of their mental state. Once received, relevant data from text messages will be manually inputted into a UoE secure server as soon as practicably possible, and then text messages will be deleted.

Data from actigraph devices will be in an anonymised form (identifiable only by participant ID), and will be transferred to a University of Edinburgh secure server by plugging the device directly into the computer via a usb socket. This will then be stored securely and only accessible to members of the research team via a password. A third appointment will be arranged in week 11 for them to return these devices (and their ketomojo devices).

